After obtaining informed consent, trained research staff will ask participants if they wish to participate in a lottery to win one of three \$150 cash prizes and record their decision on the enrollment form. Next, we will randomly assign participants to one of the 3 treatment arms. Treatments will be administered by [name] and the student investigators trained and supervised by [name]. Each participant will be assigned a unique identification number, not tied to their name, that will be used to identify their data. Assessment will consist of both physiological and psychosocial parameters. The physiological parameters will be: 1) number of acne lesions; 2) amount of sebum produced; and 3) degree of acne severity. The psychosocial factors will be: 1) dermatologic quality of life; 2) social anxiety; 3) depressive symptomatology; and 4) self-esteem. Regardless of the treatment arm assigned, each participant will complete a baseline, 3 intermediary, and 2 follow-up assessments. All assessments will be done prior to receiving treatment.

Baseline and the 2 follow-up assessment will consist of: 1) counting number of acne lesions; 2) measuring the amount of sebum produced; 3) computing the degree of acne severity (take digital photographs of the affected areas of the face and compute the severity following procedures published by Hayashi et al, [2008]); 4) dermatologic quality of life; 5) social anxiety; 6) depressive symptomatology; and 7) self-esteem. Each of these assessments will take approximately 45 to 60 minutes to complete.

Intermediary assessments will be done at week 3, 5, 6 and will include: 1) number of acne lesions; 2) amount of sebum produced; and 4) dermatologic quality of life. Each of the intermediary assessments will take approximately 15 to 25 minutes to complete.

Specific steps in the research study are as follows:

1. Using block randomization procedures, we will randomize participants into the three conditions in blocks of 6 using a computerized randomization program. The data manager will prepare a set of sealed envelopes containing the condition assignment as determined by the randomization program and place the envelopes into a box in sequential order. Select the next-in-line pre-prepared envelope and inform participant of their treatment arm. Determine if participant has sufficient time to complete the initial study visit. If not schedule the initial study visit. If yes, then continue with step 2.

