2. Conduct baseline assessment as described above.
3. Administer first treatment as per assigned arm. Within each arm, participants receive the same treatment.
 - a) **Arm 1: Photodynamic therapy with 5-aminolevulinic acid (ALA-PDT).** We will apply a formulation of ALA called Levulan[®] Kerastick to the affected areas of the participant's face. After 1 hour incubation, the affected areas will be exposed to a light source using photodynamic machine between 15 to 20 minutes. Each treatment will take approximately 90 minutes. Schedule an appointment for next treatment.
 - b) **Arm 2: Microcurrent therapy (MCT).** We will place one electrode of the microcurrent machine in one of the regional areas of the lymph nodes or affected area (i.e. the forehead) and move the second electrode systematically from the affected area towards the stationary electrode. Once the entire affected area has been covered, the staff will move the first electrode to another regional area of the lymph nodes or affected area and the process will be repeated. This will continue until all of the affected areas have been treated. This will take approximately 45 minutes. Schedule an appointment for next treatment.
4. **Arm 3: Combination therapy (ALA-PDT and MCT).** Participants will receive 3 sessions of combined photodynamic therapy with aminolevulinic acid and microcurrent therapy and 2 sessions of microcurrent therapy alone. We will first administer MCT portion of combination treatment as described in 3a followed by ALA-PDT portion as described in 3b. Schedule an appointment for next treatment. Each of these combined sessions will last approximately 135 minutes and the microcurrent therapy will last approximately 45 minutes.
5. Administer the remaining treatments as determined by condition assignment

	Arm 1	Arm 2	Arm 3
Week 1	ALA-PDT	MCT	ALA-PDT+MCT
Week 2		MCT	MCT
Week 3	ALA-PDT	MCT	ALA-PDT+MCT
Week 4		MCT	MCT
Week 5	ALA-PDT	MCT	ALA-PDT+MCT

6. Conduct remaining assessments according to the following table using measures described above

	Arm 1	Arm 2	Arm 3
Week 1	Baseline	Baseline	Baseline
Week 2			
Week 3	Intermediary assessment	Intermediary assessment	Intermediary assessment
Week 4			
Week 5	Intermediary assessment	Intermediary assessment	Intermediary assessment
Week 6	Intermediary assessment	Intermediary assessment	Intermediary assessment
Week 7	Follow-up I	Follow-up I	Follow-up I
Week 12	Follow-up II	Follow-up II	Follow-up II

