Research staff will briefly describe the study and requirements for participation. Interested individuals will be invited to complete the eligibility screener. If permission is granted, staff will administer the eligibility screen and invite all eligible individuals to enroll in the study. We will obtain written informed consent from all eligible individuals wishing to participate in the study. After obtaining informed consent, we will complete the locator/enrollment form, select the randomization envelope (See section 1), and inform participants of their condition assignment. Research staff will ascertain whether the participant has sufficient time available at the current visit to complete the baseline assessment and receive the initial treatment. This is important because the time required to complete the treatment varies by condition (See Table 1). Participant who have sufficient time will complete the baseline assessment and will be given first treatment immediately following the informed consent process. Those who do not, will be scheduled to complete these activities at a subsequent visit. Individuals who do not wish to proceed through any point described above and those who screen not eligible, will be thanked for their interest and encouraged to seek treatment at the Ziff Clinic or any other dermatology provider.

Although we anticipate that the majority of screeners will be completed face-to-face, it is possible that some individuals may contact research staff via telephone. In this case, staff will describe the study and obtain permission to conduct a preliminary eligibility screen over the telephone using the above referenced procedures. If the potential participant is eligible, we will make an in-person appointment where we will confirm eligibility by re-administering the screening questionnaire, obtain informed consent, complete locator/enrollment form, assign to treatment conditions, and administer the baseline assessment along with the first treatment. As part of the scheduling process, we will explain that the duration of the study visit will be contingent upon their condition assignment and the maximum time that may be required for the initial visit will be approximately 4 hours. Consequently, we will schedule their initial appointments at a time during which they have 4 hours available for the visit.

H3. Informed Consent Procedures.

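### Participants learn their arm before baseline is measured; baseline should be completed and locked before the envelope is opened

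*Combined protocol and SAP*

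**What the plan says.** Every description of enrolment puts assignment ahead of baseline.

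- **H2.3 Procedures for Screening and Enrollment:** "After obtaining informed consent, we will complete the locator/enrollment form, select the randomization envelope (See section 1), and inform participants of their condition assignment." Staff then check whether the person has time for baseline and the first treatment, and the section's stated reason is that treatment time differs between arms. For people short of time, "Those who do not, will be scheduled to complete these activities at a subsequent visit." The section also provides for stopping: "Individuals who do not wish to proceed through any point described above" are thanked and directed to care elsewhere.
- **2.C Part 3:** step 1 reads "Select the next-in-line pre-prepared envelope and inform participant of their treatment arm"; step 2 reads "Conduct baseline assessment as described above."
- **Assignment to Treatment Conditions (section I):** the envelope is drawn once consent and enrolment are done. Baseline is not a precondition.

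The only rule on timing, in 2.C Part 3 and in the Overview of section I, is that baseline comes before treatment.

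Telephone-screened people are given a four-hour first appointment. Face-to-face enrolments, which H2.3 expects to be the majority, have no such booking.

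On measurement, staff count lesions by visual inspection, severity is derived from those counts together with photographs, and sebum is read by an instrument. DLQI and the other psychosocial scales are self-completed on a computer. No masked assessor is described.

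**The concern.** A baseline should describe participants before assignment could affect what is recorded. Here both the participant and the enrolling staff know the arm first. A person who hoped for a different arm may rate quality of life or mood differently, and a counter who knows the arm may judge borderline lesions differently. Lesion count and DLQI are both main outcomes. Computer self-interview removes the interviewer's influence but not the participant's own knowledge.

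There are two procedural consequences. Because the time check follows disclosure, the day on which baseline is taken can depend on the arm. And someone who stops between hearing the arm and being measured is a randomised participant with no baseline or later data. A baseline recorded after disclosure is also harder to defend as an adjustment variable or as the reference for change.

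**Working it through.** The plan states no figure on this point to reproduce. The check sets out the sequence, the visit lengths, and what can be said about the planned analysis.

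**1. Sequence**

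| Step | H2.3 | 2.C Part 3 |
|---|---|---|
| Envelope opened, arm disclosed | after the enrolment form | step 1 |
| Time check | after disclosure | step 1, after disclosure |
| Baseline | after the time check | step 2 |
| First treatment | after baseline | step 3 |

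Reversing disclosure and baseline would still satisfy the rule that baseline precedes treatment.

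**2. Length of the first visit, after consent**

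Baseline duration (2.C Part 3): "Each of these assessments will take approximately 45 to 60 minutes to complete." Session durations: "Each of these combined sessions will last approximately 135 minutes and the microcurrent therapy will last approximately 45 minutes" (2.C Part 3, Arm 3). For ALA-PDT, the arm description in section I gives both about 2 hours and about 90 minutes.

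Visit = baseline (45 to 60) + session:

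| Arm | Sum | Minutes |
|---|---|---|
| MCT | 45+45 to 60+45 | 90-105 |
| ALA-PDT, 90-minute figure | 45+90 to 60+90 | 135-150 |
| ALA-PDT, 2-hour figure | 45+120 to 60+120 | 165-180 |
| Combination | 45+135 to 60+135 | 180-195 |

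The combination visit is 135 - 45 = 90 minutes longer than the MCT visit. The stated 135 minutes equals 45 + 90, so it matches the shorter ALA-PDT figure. If the 2-hour figure applied and the combined session were the simple sum, it would be 45 + 120 = 165 minutes and the visit 210-225.

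**3. Who is deferred**

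- A walk-in with 120 minutes free finishes that day in MCT (at most 105). The same person is deferred in ALA-PDT (at least 135) and in combination (at least 180).
- On the 90-minute figure, the MCT-only window is 105 to 134 minutes. From 150 to 179 minutes a person can finish in MCT or ALA-PDT but not in combination.
- On the 2-hour figure, the MCT-only window widens to 105 to 164 minutes, and the 150-179 statement no longer holds.

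**4. Why no error rate follows**

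Suppose knowledge of the arm shifts scores by d in one arm, and baseline is one of T time points in the repeated measures ANOVA. The arm-by-time interaction responds to how far that arm's shift at each time departs from its own average over time.

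- *Shift at baseline only:* the departures are d(1 - 1/T) once and -d/T at the other T - 1 points. The sum of squares is d²(1 - 1/T)² + (T - 1)d²/T² = d²(T - 1)/T.
- *Shift at every point including baseline* (current order, effect persists): all departures are 0, so nothing enters the interaction. The shift remains in the arm main effect.
- *Shift at every point except baseline* (proposed order, effect persists): the departures have the same sizes with signs reversed, so the sum is again d²(T - 1)/T.

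With six time points (lesions, sebum, DLQI) the sum is (5/6)d²; with three (severity, social anxiety, depression, self-esteem) it is (2/3)d². The same disturbance can arise under either order, depending on whether the effect lasts, and the documents do not say which applies. A shift common to all three arms cancels in any case.

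**5. Why reordering alone is not enough**

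If baseline were done first with no prior time check, the walk-in with 120 minutes would have 120 - 60 = 60 to 120 - 45 = 75 minutes left. That is enough for MCT (45) but not for ALA-PDT (90 or 120) or combination (135). The gap from baseline to first treatment would then depend on the arm.

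**The case against.** The strongest reply is that the trial is open-label throughout, so cleaning one time point changes little. For lesions, sebum and DLQI, 5 of 6 assessments come after disclosure whatever the order; for severity and the other psychosocial scales, 2 of 3 do. Unmasked assessment at those visits is the larger problem. This stands, and it limits the gain.

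Deferral also moves baseline and first treatment together, so under the current order baseline stays next to treatment in every arm. That stands too, and it is why the reordering needs a prior time check. Telephone-screened people largely escape arm-dependent deferral because of their four-hour slot, although they too are assigned before baseline.

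Three stronger readings are tempting and not supported:

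- *That the present order raises the false-positive rate by a calculable amount.* Any such figure assumes a size for the shift, which the documents do not give, and an effect at baseline only. Step 4 shows that a lasting effect reverses the comparison for the interaction test. The analysis section also does not list its time levels, so treating baseline as one of them is a natural reading, not a stated fact.
- *That dropout will differ by arm.* The plan allows people to leave after disclosure. It gives no rate, and a difference between arms is inference.
- *That the clause allowing randomisation to be adjusted to equalise arm sizes makes this worse.* That wording is loose, but it is a separate minor point and adds no weight here.

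**Conclusion.** The concern holds as a low-cost improvement to procedure. The sequence is certain: it is stated consistently and no passage requires baseline before assignment. The exposure is clear for by-eye lesion counts and the self-reported scales, partial for severity, and smaller for sebum. Arm-dependent deferral of a walk-in's baseline follows from the plan's own durations, with a 90-minute difference between the shortest and longest first visits; the exact windows depend on which ALA-PDT session length is meant.

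Neither the size nor the direction of any effect on outcomes is known. The case for change rests on having a baseline that knowledge of the arm cannot touch, and on every randomised participant having one. It does not rest on a demonstrated gain in error control.

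**What to change.** In 2.C Part 3 and H2.3:

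1. Confirm eligibility and consent. Then, before anything else, confirm that the participant has time for baseline plus the longest arm's first session (60 + 135 = 195 minutes on the stated combination figure).
2. If so, complete and lock baseline, open the envelope, and give the first treatment in the same visit.
3. If not, book the whole visit (baseline, envelope, first treatment) for a later date, so that neither deferral nor the gap from baseline to treatment depends on the arm.
4. Reconcile the two ALA-PDT session lengths, since they feed the time check, and then recheck the four-hour slot. On the stated combination figure it leaves 240 - 195 = 45 to 240 - 180 = 60 minutes for screening and consent; on the simple-sum 2-hour reading, 240 - 225 = 15 to 240 - 210 = 30.

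Requiring four free hours from everyone is not necessary. It would also rebook walk-ins with 195 to 239 minutes, who could finish on the 135-minute figure.

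The cost is protocol wording and one scheduling rule, with no new measurements, staff or participants. Walk-ins without enough time are rebooked, including some who would have drawn MCT and finished that day, so some recruitment may be lost. Some people may give 45 to 60 minutes to baseline and then decline before assignment. Only the baseline time point is protected; later assessments remain open-label.

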2.A. Overview of Proposed Subjects/Participants

(complete all that apply and provide maximum number proposed within each category):

Subject Group	Fetus in Utero/ non-viable fetuses/ abortuses	Newborns or Infants	Children (aged 2-6)	Children (age 7-12)	Adolescents (aged 13-17)	Adults (18+)	Pregnant Women	Adults with Guardians
Mark X for each proposed subject type						X		
# of Proposed Subjects*						60		

Please briefly describe your potential subjects:

Participants will be males and females with mild to moderate facial acne (mild to moderate acne is operationally defined as being acne severity grade 2-4 on the Leeds grading system). To be eligible, participants must: 1) be ages 18 to 30; 2) have mild to moderate facial acne; 3) have skin type II-V as measured in the Fitzpatrick Scale; 4) be able to understand written and/or spoken English; and 5) be able to provide written informed consent.

*By proposed subjects, the IRB means subjects who will consent to be in the study and begin the study activities.

2.B. Subject Vulnerability

Do any subjects have limited decision-making autonomy, have communication problems that would limit ability to dissent to study procedures, belong to a group that is vulnerable to coercion, or belong to a group defined by regulation as requiring greater care?

Yes	No
	

If you indicated "Yes", please mark with an X next to each applicable category in the column to the right and complete the remainder of this section

Prisoners	
Pregnant Women	
Cognitive impairment or emotional problems that potentially limit decision making	
Communication impairments that may preclude communicating a decision to discontinue participation or refuse participation	
Students of the investigator or investigator's department	
Employees of the investigator or investigator's department	
Children (minors)	
Terminally ill	

Other (specify):

--

If you indicated any of the above, please justify your rationale for including these subjects.

--

If you are using potentially vulnerable subjects as described above (infants, children, pregnant women/fetuses, terminally ill, decision-impaired, communication-impaired, students/employees, or prisoners), does the research create greater than minimal risk?

Yes	No
	

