efficacy of combination photodynamic therapy with 5-aminolevulinic acid and microcurrent therapy for the treatment of acne vulgaris. We will recruit up to 60 males and females and randomly assign them to one of 3 treatment arms (*photodynamic therapy with 5-aminolevulinic acid (ALA-PDT)*; *microcurrent therapy (MCT)*; and *combination therapy (ALA-PDT and MCT)*). (See Table 1.) All participants will complete a baseline assessment prior to initiating treatment and two follow-up assessments at 4 weeks and 12 weeks post termination of treatment. During the treatment phase, we will conduct intermediary assessments to help us track the progression of the treatment over time at weeks 3 and 5 as well as 1 week post the termination of the treatment (week 6). We will conduct both physiological and psychosocial assessments; the content of the intermediary assessment will be much less than the other 3 assessments to reduce participant data. The most comprehensive assessments will be conducted at baseline and the 2 follow-up points and will consist of all of the physiological and psychosocial factors as well as demographic factors that will be collected exclusively at the baseline assessment. At the intermediary assessments we will collect the number of acne lesions, amount of sebum produced and dermatologic quality of life. Psychosocial data will be collected via computer-assisted self-interviews (CASI). Physiological data will be entered into the computer program by research staff.

Table 1. Frequency and duration of study visits (assessment(s) and treatment(s))

	ALA-PDT	MCT	ALA-PDT+MCT
Week 1	✓	✓	✓+✓
Week 2		✓	✓
Week 3	✓	✓	✓+✓
Week 4		✓	✓
Week 5	✓	✓	✓+✓

12. Description of the ALA-PDT treatment arm

In this arm participants will receive 3 ALA-PDT treatments at 2 week intervals. The duration of each treatment will be approximately 2 hours. At each treatment, we will apply a formulation of ALA called Levulan® Kerastick (manufactured by Dusa Pharmaceuticals, MA, USA) to the affected areas of the participant's face (See Figure 2). After 1 hour incubation, the affected areas will be exposed to a light source using photodynamic machine between 15 to 20 minutes. (See Figure 2). Each treatment will take approximately 90 minutes. At the completion of each treatment session, participants will be counseled to follow the photo-protection measures.

Figure 2. Levulan® Kerastick and Photodynamic Therapy Machine*

[figure not shown]

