* If respondent does not remember their medication ask the following probes:

- can you describe the medication... is it a pill? Is it a cream or lotion that you put on your skin?
How often do you use it? If the respondent still cannot remember explain that this information is important and ask them to provide it by contacting the research team, asking their provider, or other reasonable steps.

(Continue screening but do not enroll because eligibility cannot be determined)

8. Do you have history of photo-sensitive dermatitis?

Yes No (if yes, INELIGIBLE but continue screener)

9. Do you have a pacemaker?

Yes No (if yes, INELIGIBLE but continue screener)

Eligible and enrolled

_____ Eligible not interested

_____ Ineligible

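### The H2.3 exit rule extends past randomisation: a person who declines after learning the arm leaves like a screen failure, with no instruction to record why, assess them or report them by arm

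*Combined protocol and SAP*

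**What the plan says.** H2.3 (Procedures for Screening and Enrollment) runs in this order: describe the study, screen, obtain consent, complete the locator/enrollment form, then "select the randomization envelope (See section 1), and inform participants of their condition assignment". Only then do staff check whether the participant has time for baseline and first treatment. Of people without enough time it says: "Those who do not, will be scheduled to complete these activities at a subsequent visit". The step list in 2.C Part 3 agrees, with assignment as step 1 and baseline as step 2.

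The same H2.3 paragraph closes with the exit rule: "Individuals who do not wish to proceed through any point described above and those who screen not eligible, will be thanked for their interest". They are also encouraged to seek treatment at the Ziff Clinic or another dermatology provider.

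Other relevant places:

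- The Screener form has three dispositions: eligible and enrolled, "Eligible not interested", and ineligible.
- Assignment to Treatment Conditions describes sequential sealed envelopes in blocks of 6. It lets staff adjust the procedure to keep arm sizes equal, with no rule for doing so.
- The analysis text (3.M, and Data Management, Analysis and Quality Assurance Procedure) names repeated measures ANOVA. It gives no analysis set, no missing-data rule and no reporting of post-assignment refusals.

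**The concern.** The steps that precede the exit rule include opening the envelope and disclosing the arm. Read as written, the rule therefore gives a randomised participant who backs out the same exit as someone who was never eligible. Once the arm is known, the decision to stay can depend on it. If such people are released without assessment or arm-level reporting, the people analysed in each arm are those who accepted that arm, and a reader of the results could not judge how far this departs from the randomised groups.

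Aim 3 (Ho3a and Ho3b) compares combination with each monotherapy. Combination has the longest visits and sits in both contrasts. The arms are also described differently: ALA-PDT is called standard treatment, while the protocol found no published use of MCT in acne. Participants may have preferences as well as time limits.

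**Working it through.** The documents give no refusal rate, sample-size calculation or analysis set, so there is no stated figure to reproduce. The check has three parts.

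**1. Where a decliner stands.** The sequence is consent, enrollment form, envelope, disclosure, time check, baseline, first treatment. A person who stops between disclosure and baseline has been randomised but has no baseline or later value. Repeated measures ANOVA uses values over time, so this person contributes nothing to it. No available section tells staff to follow them, log the reason, or report them by arm.

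**2. Whether burden differs by arm.** Inputs: baseline 45–60 min (2.C Part 3); MCT session 45 min; combination session 135 min; ALA-PDT session 90 min, although the same ALA-PDT description also says about 2 hours. First visit = baseline + session.

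| Arm | First visit (min) | Total treatment time (min) |
|---|---|---|
| MCT | 45+45 to 60+45 = 90–105 | 5×45 = 225 |
| ALA-PDT, 90 min | 45+90 to 60+90 = 135–150 | 3×90 = 270 |
| ALA-PDT, 2 hours | 45+120 to 60+120 = 165–180 | 3×120 = 360 |
| Combination | 45+135 to 60+135 = 180–195 | 3×135 + 2×45 = 495 |

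The stated 135 min equals 45+90, so it matches the 90-minute figure. If 2 hours applied, the combined session would be 45+120 = 165 min and its first visit 210–225 min. The two ALA-PDT durations must be reconciled. On either figure, the combination visit is at least about twice the MCT visit.

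**3. What refusals could do (assumptions only).** The plan says "We will recruit up to 60 males and females and randomly assign them to one of 3 treatment arms". Blocks of 6 over three arms imply equal allocation, so 60/3 = 20 per arm at full recruitment. Let r be the share of an arm that declines and D the difference in mean outcome between those who stay and those who decline. The full-arm mean is (1−r)×stay + r×decline, so the mean among those who stay differs from it by r×D.

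- 2 of 20: r = 10%; for D from 0.25 to 1.0 SD, the shift is 0.025 to 0.10 SD.
- 5 of 20: r = 25%; for the same D, the shift is 0.0625 to 0.25 SD.

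Neither r nor D comes from the documents. Equal r and equal D in two arms would cancel in the contrast between them; unequal values would not.

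**The case against.** The case on the other side has several parts.

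- **Denominator.** A reader might infer that decliners are dropped from the denominator and that the report would show no loss after randomisation. The documents do not say so. H2.3 says how to take leave of people who stop; it does not say how to count them. The inference rests on silence, and the consent pages, which might contain withdrawal wording, are not available.
- **Lost arm.** A reader might infer that the assignment itself disappears. It need not. The enrollment form precedes the envelope, the envelopes are sequential, and the assignment section regards the person at that moment as newly enrolled. The screener is completed before consent, so its lack of a post-randomisation category is unsurprising. What clearly has no stated place is the reason for leaving.
- **The definition in 2.A.** The wording "subjects who will consent to be in the study and begin the study activities" might be read as an analysis set. It is the IRB form's own note on which number to enter.
- **Missed first visits.** These might be thought to fall under the exit rule. The rule covers people who do not wish to proceed; people short of time are rescheduled.
- **Mitigation.** For those screened by telephone, the plan says: "Consequently, we will schedule their initial appointments at a time during which they have 4 hours available for the visit". That is 240 min, longer than any first visit computed above. This reduces time-driven refusal, but H2.3 expects most screening to be face-to-face, and a long slot does not address preference for an arm.
- **Direction.** Burden points to more refusals of combination, while a wish for the established treatment points to refusals of MCT alone. The direction of any bias is unknown.
- **Referral.** The exit does not simply send people away from the study site, since the Ziff Clinic is one of the options named.

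All of these limits stand. They do not remove the literal reach of the rule past the envelope, or the absence of any text that keeps decliners in view.

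**Conclusion.** The concern holds in a limited form. H2.3 contains an exit rule that, as written, releases randomised decliners in the same way as screen failures, before any baseline value exists, and no available section retains, follows or reports them by arm. This is more than a missing detail, because the one instruction that does exist works against the randomised comparison. Exclusion from the analysis is a risk left open and is not a stated policy.

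Differential refusal is plausible from the protocol's own visit times. Its rate, direction and effect on the contrasts are unknown; the 10% to 25% and the SD shifts are illustrations that assume 20 per arm. The remedy does not depend on those numbers and should be in place before the first envelope is opened, since reasons for refusal are hard to reconstruct afterwards.

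**What to change.** In H2.3, limit the exit rule to people who stop before the envelope is opened. Then state that, from opening onwards:

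- the person is a randomised participant and counts in the assigned arm within the 60;
- staff log ID, arm, date and reason for declining;
- the envelope is not reused or replaced, and the permission to adjust arm sizes does not override this;
- the person is invited to the baseline and follow-up assessments even if they decline treatment, voluntarily and with the right to withdraw respected;
- post-assignment refusals are reported by arm.

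Add a line to the enrollment record for people randomised who declined after assignment, with arm and reason. Add a sentence to the analysis section that everyone whose envelope was opened belongs to the randomised set.

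Completing baseline before opening the envelope would further reduce the loss: a decliner would at least have baseline values. It would not supply their outcomes, and it means changing the order in both H2.3 and 2.C Part 3.

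The cost is a few sentences and one form line. Some of the 60 places may go to people who take no treatment, and reported attrition will look worse.
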